3 STUDY DESIGN

This is a Phase 2, two-stage study of the safety and efficacy of pracinostat in combination with azacitidine in patients with IPSS-R high and very high-risk MDS who are previously untreated with HMAs. Enrollment in this study will be limited to high/very high-risk MDS because this group represents the highest unmet need, with median survival of less than 18 months.

Recognizing that additional safety and efficacy of pracinostat plus azacitidine is desirable before evaluating the treatment regimen in a placebo-controlled environment, the protocol is being amended to become a 2-stage open-label study comprising Stage 1 and Stage 1 expansion (Stage 1b).

Stage 1 will be conducted as an open-label single arm in approximately 40 evaluable subjects to assess if the pracinostat dose regimen results in a discontinuation rate that meets a predefined threshold, and the observed efficacy justifies expansion of enrollment in Stage 1b.

A discontinuation rate of approximately $\leq 10\%$ in Stage 1, a rate comparable to that observed with azacitidine alone in Study MEI-003, would support expansion to Stage 1b. Stage 1b will be conducted as an open-label arm to achieve a total enrollment of approximately 60 subjects evaluable for efficacy, inclusive of Stage 1 and Stage 1b enrollment.

Study drugs should be continued until disease progression or intolerable toxicity. It is important to note that the median time to achieving a response with azacitidine alone is 4 to 5 months. Therefore, early (< 6 months) discontinuation of study therapy for ‘no response’ should be avoided. The Medical Monitor should be contacted by the Investigator prior to discontinuing study drugs in a subject from the study to discuss the rationale for discontinuation.

After discontinuing study drugs, subjects will be followed every 3 months (± 1 month) until death or study termination to collect information on disease status (i.e., improvement of disease

response or disease progression), start of non-protocol therapies (e.g., stem cell transplant or an MDS-directed therapy) and survival.

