5.2 Study Treatment

Study visits should occur on a 28-day schedule. A -4 day to +7-day window is allowable for each clinic visit to accommodate subject request, holidays, weekends, inclement weather, or other unforeseen circumstances.

Pracinostat is to be taken in the morning on an empty stomach or following a light meal once a day on Days 1, 3, and 5 (Week 1); Days 8, 10, and 12 (Week 2); and Days 15, 17, and 19 (Week 3); with a week of rest during Week 4. Pracinostat will be administered in the clinic on Day 1 of Cycle 1, and subjects may self-administer at home on all other days. Pracinostat is to be taken before azacitidine. Missed doses of pracinostat should not be made up (refer to [Section 3.1.1](#)). To monitor pracinostat dosing, subjects will be given a dosing diary card to track medication compliance.

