5.2.1 Day 1, All Cycles

The following procedures and assessments will be performed on Day 1:

- Update of transfusion history for 8 weeks prior to first study drug administration on Cycle 1 Day 1 only
- Physical examination
- Vital signs
- Smoking assessment (for subjects enrolled under Amendment 1)
- ECOG performance status determination
- AE assessment
- Concomitant medication review
- 12-lead ECG performed in triplicate approximately once every 5 to 10 minutes to calculate the QTcF interval. On Day 1 of Cycle 1, ECGs will be obtained pre-dose, pracinostat will be taken, and azacitidine will be administered. Ninety minutes (\pm 15 minutes) post-pracinostat dosing, triplicate ECGs will be repeated. Beyond Cycle 1, non-triplicate ECGs will be performed as clinically indicated.

- Administer pracinostat.
- CBC with differential and blasts.
- Serum chemistry: glucose, BUN, creatinine, sodium, potassium, chloride, calcium, CO₂, ALP, AST, ALT, total bilirubin, total protein, albumin, and LDH.
- Dispense study medication. Following Cycle 1, study medication compliance will be assessed on Day 1 of each cycle.
- Azacitidine administration.
- Response assessments (after Cycle 2 and Cycle 6; see Section 5.2.4).

5.2.2 *Days 2–9, All Cycles*

- AE assessment on each day of azacitidine administration.
- Azacitidine administration (see [Section 3.1.2](#)).

5.2.3 *Day 15 and Day 22 (Cycles 1 and 2 only)*

- Vital signs.
- Smoking assessment (for subjects enrolled under Amendment 1).
- AE assessment.
- Concomitant medication review (Day 22 only).
- CBC with differential and blasts. A manual differential is preferred but is not required at these visits.
- Serum chemistry: glucose, BUN, creatinine, sodium, potassium, chloride, calcium, CO₂, ALP, AST, ALT, total bilirubin, total protein, albumin, and LDH.

5.2.4 *Response Assessments*

To assess hematologic response, CBC with differential including blast cell counts will be obtained every Cycle Day 1 (-4 days to +7 days), and when response assessments and confirmations are scheduled to be performed ([Appendix A](#)).

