Proposed Modified International Working Group Response Criteria for Altering Natural History of MDS	
Category	Response Criteria (responses must last at least 28 days)
Complete remission	
Bone marrow: $\leq 5\%$ myeloblasts with normal maturation of all cell lines*
 
Persistent dysplasia will be noted*†
 
Peripheral blood‡
 
Hemoglobin ≥ 11 g/dL
 
Platelets $\geq 100 \times 10^9/L$
 
Neutrophils $\geq 1.0 \times 10^9/L$†
 
Blasts 0%

Partial remission	
All CR criteria if abnormal before treatment except:
 
Bone marrow blasts decreased by $\geq 50\%$ over pretreatment but still $> 5\%$
 
Cellularity and morphology not relevant

Marrow CR†	
Bone marrow: $\leq 5\%$ myeloblasts and decrease by $\geq 50\%$ over pretreatment†
 
Peripheral blood: if HI responses, they will be noted in addition to marrow CR†

Stable disease	Failure to achieve at least PR, but no evidence of progression for > 8 weeks
Failure	Death during treatment or disease progression characterized by worsening of cytopenias, increase in percentage of bone marrow blasts, or progression to a more advanced MDS FAB subtype than pretreatment
Relapse after CR or PR	
At least 1 of the following:
 
Return to pretreatment bone marrow blast percentage
 
Decrement of $\geq 50\%$ from maximum remission/response levels in granulocytes or platelets
 
Reduction in hemoglobin concentration by ≥ 1.5 g/dL or transfusion dependence

Cytogenetic response	
Complete: Disappearance of the chromosomal abnormality without appearance of new ones
 
Partial: At least 50% reduction of the chromosomal abnormality

Disease progression	
For patients with:
 
Less than 5% blasts: $\geq 50\%$ increase in blasts to $> 5\%$ blasts
 
5% – 10% blasts: $\geq 50\%$ increase to $> 10\%$ blasts
 
10% – 20% blasts: $\geq 50\%$ increase to $> 20\%$ blasts
 
20% – 30% blasts: $\geq 50\%$ increase to $> 30\%$ blasts
 
Any of the following:
 
At least 50% decrement from maximum remission/response in granulocytes or platelets
 
Reduction in hemoglobin by ≥ 2 g/dL
 
Transfusion dependence

Survival	
Endpoints:
 
Overall: death from any cause
 
Event free: failure or death from any cause
 
PFS: disease progression or death from MDS
 
DFS: time to relapse
 
Cause-specific death: death related to MDS

Reference: [Cheson 2006](#).

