9.2.1 Clinical Response

Clinical response rates will be based on the best response achieved by each patient in the following hierarchy:

CR -> PR -> Marrow CR -> SD -> PD

The response rate is based on confirmed response, the following rules will be taken into account:

If a patient has 2 CRs at least 28 days apart, best response is CR;

If a patient has at least 1 PR followed by 1 CR at least 28 days later, but no subsequent CR (ie the CR is not confirmed), best response is PR;

If a patient has 2 PRs at least 28 days apart, but no subsequent CRs, best response is PR;

If a patient has at least 1 Marrow CR followed by 1 CR or PR at least 28 days later, but no subsequent CR or PR (ie the CR/PR is not confirmed), best response is Marrow CR;

If a patient has 2 Marrow CRs at least 28 days apart, but no subsequent CRs or PR, best response is Marrow CR;

If a patient has 2 stable disease (SD) at least 28 days apart, but no subsequent PD, best response is SD.

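### SAP 9.2.1 withdraws best response SD whenever PD follows, contradicting its own hierarchy and the SD definition in Protocol Appendix D

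*SAP*

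**What the plan says.** SAP 9.2.1 opens with the principle: "Clinical response rates will be based on the best response achieved by each patient in the following hierarchy". The order given is "CR -> PR -> Marrow CR -> SD -> PD". Rules for confirmed responses follow, and the one for SD is: "If a patient has 2 stable disease (SD) at least 28 days apart, but no subsequent PD, best response is SD". The rule for CR carries no condition on what happens afterwards: "If a patient has 2 CRs at least 28 days apart, best response is CR". The PR and Marrow CR rules do use a 'no subsequent' clause, but it refers only to better responses.

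The response criteria table in Protocol Appendix D defines SD as "Failure to achieve at least PR, but no evidence of progression for > 8 weeks".

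SAP section 9 calls for a frequency summary of disease response and a by-subject response listing. SAP 8.6.2 also lists the best response of each transplanted subject. SAP section 13, on changes from the protocolled analysis, covers the OS censoring date and the naming of populations. It does not mention SD.

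**The concern.** Best response should not depend on what happens after it has been reached. Under this SAP a later PD leaves CR, PR and Marrow CR intact, and SD alone can be revoked by a later, worse result. The neighbouring rules suggest that the clause was meant to exclude a later CR, PR or Marrow CR and that PD was written by mistake.

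Progression after a period of stability is an ordinary course in this trial. The Protocol's study design section says "Study drugs should be continued until disease progression or intolerable toxicity", and progression is still recorded at three-monthly follow-up after treatment stops. The longer a stable subject is followed, the more likely the SD label is lost.

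At stake are the SD and PD rows of the response summary. Two programmers could fill them differently from the same SAP. If SD-then-PD subjects are counted as PD, a reader will take them for subjects who never had disease control.

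**Working it through.** The documents state no SD or PD rate, so there is no figure of the plan's to reproduce. The check has four parts.

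**1. The rules applied to one subject.** Take a subject with SD at the end of Cycle 2, SD at the end of Cycle 6, and PD later.

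- Hierarchy: the best result achieved is SD.
- SD rule: PD followed, so SD is not given.
- Appendix D: no progression for more than 8 weeks, so SD.
- Other rules: none assigns this subject to PD or to anything else.

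Replace the two SDs with two CRs and keep the later PD: best response is CR. The conflict is specific to SD.

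**2. The 28-day interval against 8 weeks.** Protocol 5.2.1 schedules response assessments after Cycles 2 and 6, and Protocol 5.2 says "A -4 day to +7-day window is allowable for each clinic visit".

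- End of Cycle 2: 2 × 28 = Day 56, window Day 52 to Day 63.
- Earliest second SD: 52 + 28 = Day 80; nominal 56 + 28 = Day 84. Both exceed 56 days.
- Next scheduled marrow: 6 × 28 = Day 168.

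On the planned schedule, two SDs at least 28 days apart already imply more than 8 weeks from Day 1. A shortfall arises only if SD is recorded at an earlier unscheduled visit, or if the 8 weeks are counted from the first SD.

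**3. How many SD subjects could be affected.** Inputs from the documents:

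- Enrolment over 24 months and analysis 12 months after the last subject (Protocol section 3), so 12 to 36 months of follow-up per subject.
- Median EFS of 9 months in MEI-003 (Protocol 1.5). It covers all subjects and counts deaths, so it is only a stand-in for SD subjects.

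Assumptions: exponential event times, uniform enrolment, every PD documented, and a fixed share of first events that are PD rather than death.

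With λ = ln 2 / median and t₀ the time at which SD is established, the share with a later event, averaged over follow-up, is

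1 − [exp(−λ(12 − t₀)) − exp(−λ(36 − t₀))] / (24λ)

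For a median of 9 months, λ = 0.0770 and 24λ = 1.848.

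- t₀ = 2 months: 1 − (0.463 − 0.073)/1.848 = 0.79. Times 0.6 and 0.8: 47% and 63%.
- t₀ = Day 84 (84/30.4375 = 2.76 months): 1 − (0.491 − 0.077)/1.848 = 0.78. Times 0.6 and 0.8: 47% and 62%.

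Other inputs, with t₀ = Day 84:

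| Median event time, follow-up | PD share 100% | 80% | 60% | 50% |
|---|---|---|---|---|
| 6 months, 12 to 36 months | 88% | 71% | 53% | 44% |
| 9 months, 12 to 36 months | 78% | 62% | 47% | 39% |
| 15 months, 12 to 36 months | 61% | 48% | 36% | 30% |
| 9 months, 12 months only | 51% | 41% | 31% | 25% |

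The table runs from 25% to 88%. These are scenarios, not bounds: a 15-month median with 12 months of follow-up and a 50% PD share gives 35% × 0.5 = 17%.

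**4. What changes in the results.** SD and PD are both non-response for ORR and CR rate, and neither counts toward the clinical benefit rate. DOR, EFS, PFS and OS are built from dates of response, progression and death, not from the best-response category. Only the SD and PD rows, and any listing that carries the derived category, depend on the rule.

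**The case against.** The strongest defence is that little turns on this. The SD rate is not an objective or endpoint, no formal testing is planned, and the by-subject response listing may show the SD-then-PD sequence to anyone who looks. All of that stands and limits the point to a minor one. It does not remove the contradiction, because the response summary still has to put each subject in one row.

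A reader might go further and infer that most stable subjects will be reported as PD. The documents do not support that. The SAP never assigns PD to these subjects; it leaves two conflicting answers. No PD rate among SD subjects is given, and the scenarios fall on both sides of one half. The model also assumes that every later PD is recorded, whereas Protocol 5.4 allows telephone follow-up and makes the blood count optional, so the true share could be lower.

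A reader might also infer that SD is accepted after only 28 days. The 28 days are a gap between two assessments, not a duration from Day 1, and on the planned schedule the second SD falls on Day 80 or later. The figure also matches the 28-day minimum in the heading of the Appendix D table. What remains is a difference in wording from Appendix D that should be closed.

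**Conclusion.** Wrong as written, minor. The condition on later PD in SAP 9.2.1 contradicts the hierarchy in the same section, departs from Appendix D, and is not declared in SAP section 13. This rests on the text alone.

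The size rests on assumptions. Roughly 47% to 63% of SD subjects could be affected with a 9-month median event time and PD as 60% to 80% of first events, and about 25% to 88% across the other inputs tabulated. The effect is an understated SD row and an overstated PD row if the programmer counts these subjects as PD, and no effect if the programmer follows the hierarchy. No efficacy endpoint named in the Protocol or SAP changes.

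**What to change.** Replace the SD rule in SAP 9.2.1 with:

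> A subject with two SD assessments 28 days or more apart, no progression seen for more than 8 weeks counted from Day 1, and no confirmed CR, PR or Marrow CR has best response SD, regardless of later PD. PD is best response only if progression occurs before SD is established.

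This keeps the two-assessment confirmation. The 8-week test brings the SAP into line with Appendix D and has little effect on the planned visit schedule.

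Add a line giving the category for a subject with a single SD, both where PD follows and where no further assessment follows. Without it, a subject who leaves after the end-of-Cycle-2 assessment has no row.

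The cost is two or three sentences in the SAP and the matching change to the best-response derivation before database lock. No new data are needed.

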9.2.1.1 Complete Response (CR) rate

Complete Response (CR) rate will be defined as the proportion of subjects with confirmed CR (i.e. 2 CRs at least 28 days apart) according to IWG criteria, as defined in section 2.3.2. Subjects achieving IWG criteria on bone marrow ($\leq 5\%$ myeloblasts with normal maturation of all cell lines), achieving IWG criteria on Peripheral blood at next 6 cycles, and confirmed achieving IWG criteria on Peripheral blood again with at least 28 days apart will be defined as achieving CR.

Subjects who are not evaluable for response for any reason will be considered as not achieving CR. The response rate and associated 95% confidence interval will be calculated using an exact binomial distribution approach for the ITT, EE and PP populations.

9.2.1.2 Overall hematologic improvement (HI) response rate

Overall hematologic improvement (HI) response rate will be defined as the proportion of subjects who demonstrate confirmed major hematologic improvement as defined by IWG criteria (i.e. 2 HIs at least 8 weeks apart), for at least one criterion. Only subjects with pre-treatment abnormal values will be considered for this endpoint. The response rate and associated 95% confidence interval will be calculated using an exact binomial distribution approach for the ITT, EE and PP populations.

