Abbreviations: CR = complete response; DFS = disease-free survival; FAB = French-American-British; MDS = myelodysplastic syndrome; PFS = progression-free survival; PR = partial response

Deletions to IWG response criteria are not shown. To convert hemoglobin from g/dL to g/L, multiply g/dL by 10.

* Dysplastic changes should consider the normal range of dysplastic changes (modification) ([Ramos et al. 1999](#))

† Modification to IWG response criteria.

‡ In some circumstances, protocol therapy may require the initiation of further treatment (e.g., consolidation, maintenance) before the 4-week period. Such patients can be included in the response category into which they fit at the time the therapy is started. Transient cytopenias during repeated chemotherapy courses should not be considered as interrupting durability of response, as long as they recover to the improved counts of the previous course.

Modified IWG Response Criteria for Hematological Improvement	
Hematological Improvement*	Response Criteria (responses must last at least 8 weeks) †
Erythroid response (pretreatment, < 11 g/dL) (HI-E)	Hemoglobin increase by ≥ 1.5 g/dL Relevant reduction of units of RBC transfusions by an absolute number of at least 4 RBC transfusions/8 weeks compared with the pretreatment transfusion number in the previous 8 weeks. Only RBC transfusions given for a hemoglobin of ≤ 9.0 g/dL pretreatment will count in the RBC transfusion response evaluation‡
Platelet response (pretreatment, < 100×10^9 /L) (HI-P)	Absolute increase of $\geq 30 \times 10^9$ /L for patients starting with $> 20 \times 10^9$ /L platelets Increase from $< 20 \times 10^9$ /L to $> 20 \times 10^9$ /L and by at least 100%†
Neutrophil response (pretreatment, < 1.0×10^9 /L) (HI-N)	At least 100% increase and an absolute increase $> 0.5 \times 10^9$ /L†
Progression or relapse after HI‡	At least 1 of the following: 
• At least 50% decrement from maximum response levels in granulocytes or platelets• Reduction in hemoglobin by ≥ 1.5 g/dL• Transfusion dependence

Abbreviations: HI = hematologic improvement; RBC = red blood cell;

Deletions to the IWG response criteria are not shown.

To convert hemoglobin levels from g/dL to g/L, multiply g/dL by 10.

* Pretreatment counts averages of at least 2 measurements (not influenced by transfusions) ≥ 1 week apart (modification).

† Modification to IWG response criteria.

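### The SAP's rule for confirmed HI needs only two assessments at least 8 weeks apart, so improvement that was lost in between, or seen in different lineages, can be counted as response

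*SAP*

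**What the plan says.** **Protocol.** Appendix D has two response tables, and both state a duration. The hematological improvement table is headed "Response Criteria (responses must last at least 8 weeks", and the natural-history table (CR, PR, marrow CR) is headed "Response Criteria (responses must last at least 28 days". Its footnotes excuse some interruptions. For the natural-history table, "Transient cytopenias during repeated chemotherapy courses should not be considered as interrupting durability of response", provided counts recover. Progression or relapse after HI is judged only where there is no other explanation, such as acute infection, chemotherapy courses, gastrointestinal bleeding or hemolysis. Section 5.2.4 schedules a CBC on Day 1 of every cycle.

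**SAP.** Section 9.2.1.2 defines the HI response rate by "confirmed major hematologic improvement as defined by IWG criteria (i.e. 2 HIs at least 8 weeks apart), for at least one criterion". Section 9.2.1 gives matching rules for the other categories: "If a patient has 2 CRs at least 28 days apart, best response is CR" and "If a patient has 2 PRs at least 28 days apart, but no subsequent CRs, best response is PR". A condition on progression is written for stable disease only: "If a patient has 2 stable disease (SD) at least 28 days apart, but no subsequent PD, best response is SD". Section 9.2.1.1 allows the blood criteria for CR to be met after the marrow criteria, "achieving IWG criteria on Peripheral blood at next 6 cycles", and then confirmed at least 28 days later.

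**Where HI is used.** Under SAP 9.2.1.3, HI alone makes a subject a CBR responder. SAP 2.3.2 adds a second DOR analysis that includes HI and starts at the first determination of response.

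**The concern.** A response that lasts 8 weeks and a response seen at two dates 8 weeks apart are different events. The second includes every case of the first. It also includes cases where the count fell back below the threshold between the two dates. The SAP sets no upper limit on the gap, so the two dates may lie anywhere in the treatment period.

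The phrase about at least one criterion can also be read as letting a platelet HI at one visit and a neutrophil HI at another confirm each other.

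At stake are the HI rate, the CBR and the DOR analysis that includes HI. In that DOR analysis, an isolated first HI can start the clock. Data already collected on Day 1 of the cycles in between would be ignored.

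**Working it through.** **Step 1: the rules side by side.**

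| | Appendix D | SAP |
|---|---|---|
| HI | lasts at least 8 weeks | two HIs at least 8 weeks apart |
| CR, PR, marrow CR | lasts at least 28 days | two assessments at least 28 days apart |
| Loss in between | excused only for listed causes | not mentioned |
| Maximum gap | not needed, since response is continuous | none |
| Same lineage for HI | criteria set out lineage by lineage | not stated |

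**Step 2: does the gap contain data?** Cycles last 28 days, so Day 1 of Cycle 3 and Day 1 of Cycle 5 are 2 × 28 = 56 days (8 weeks) apart, with the Cycle 4 Day 1 CBC between them. Suppose hemoglobin is up by at least 1.5 g/dL at Cycles 3 and 5 but by less than 1.5 g/dL at Cycle 4. The SAP rule confirms HI-E. An improvement that must last 8 weeks is not shown, unless a listed exception explains the dip. There is not always a CBC in between: Appendix A allows a delay of up to 4 weeks for toxicity, so two adjacent Day 1 visits can be 28 + 28 = 56 days apart.

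**Step 3: illustration of size.** The documents give no per-visit probability, so the following are assumptions: one lineage, 10 four-weekly visits (Protocol section 3 expects a median of about 10 cycles), and no early stopping. A sustained HI means three consecutive qualifying visits (weeks 0, 4, 8). The any-two rule means that the first and last qualifying visits are at least two visits apart.

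*Independent visits, probability q at each.* The any-two probability is 1 − (1−q)^10 − 10q(1−q)^9 − 9q²(1−q)^8. The three subtracted terms are no qualifying visit, exactly one, and exactly two that are adjacent. For q = 0.10 this is 1 − 0.3487 − 0.3874 − 0.0387 = 0.225. The sustained probability comes from enumerating all visit patterns.

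*Persistent response.* Here e is the chance of entering response at a visit and s the chance of staying in it at the next. All subjects start out of response. Simulation with 100,000 subjects gave the figures below. Exact enumeration agrees with each to within about 0.2 points.

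| Assumption | Any two | Sustained | Difference (points) |
|---|---|---|---|
| e = 0.10, s = 0.9 | 50.0% | 48.1% | 1.9 |
| e = 0.10, s = 0.7 | 38.6% | 31.5% | 7.1 |
| e = 0.10, s = 0.5 | 30.2% | 17.1% | 13.1 |
| e = 0.20, s = 0.9 | 77.5% | 73.6% | 3.9 |
| e = 0.20, s = 0.7 | 67.9% | 51.2% | 16.7 |
| e = 0.20, s = 0.5 | 61.5% | 29.4% | 32.1 |
| independent, q = 0.05 | 7.1% | 0.1% | 7.0 |
| independent, q = 0.10 | 22.5% | 0.7% | 21.8 |
| independent, q = 0.20 | 56.4% | 5.2% | 51.2 |

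Every difference is positive, as it must be, because every sustained pattern also satisfies the any-two rule. The model leaves out the Appendix D exceptions, which would narrow the gap, and confirmation across lineages, which would widen it.

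**Step 4: CR and PR.** In the same model, any two visits at least 28 days apart are compared with two consecutive visits. With e = 0.10 the results are 57.4% v 56.8% (s = 0.9), 49.8% v 47.2% (s = 0.7) and 41.9% v 35.6% (s = 0.5), differences of 0.6, 2.6 and 6.3 points. This does not include the stopping of treatment at relapse or progression, which would reduce them further.

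**The case against.** **The IWG criteria still apply.** SAP 9.2.1.2 refers to them, and they carry the duration. The two-assessment wording may only describe how confirmation is recorded, and the lineage phrase may well be meant as two HIs in the same criterion. This stands so far as it goes: the text shows that non-lasting HI can be counted, not that it will be. It does not remove the point. The words in brackets state what confirmation means, and a programmer would code them.

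**A response is an investigator's assessment, not a raw count.** Protocol 5.2.4 says so for the primary efficacy analyses, and one HI-E route is a reduction in transfusions over 8 weeks, which a visit-by-visit model cannot represent. This stands, and it is why the table shows direction and range only.

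**A large loss would be caught elsewhere.** Appendix D treats a halving of granulocytes or platelets from the best level, a hemoglobin fall of at least 2 g/dL, or transfusion dependence as disease progression, and Protocol 4.3 lists documented progression as a reason to stop treatment. This also stands. The exposure is to smaller losses that fall below the HI threshold without being progression.

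**Tempting stronger reading: the primary ORR is inflated.** A reader might note that 24/60 has an exact lower limit of 27.6%, as the SAP states, and that 22/60 gives 24.6%, so two reclassified responders would take the limit below the 25% benchmark. The arithmetic is right, but the documents give no reason to expect those reclassifications. Protocol 9.3.1 itself defines confirmed CR as two CRs at least 28 days apart. Relapse after CR or PR is a reason to stop treatment. Visits 28 days apart have no scheduled CBC between them after Cycle 2. Cytopenias that recover are excused.

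**Conclusion.** The point holds for HI. The counting rule in SAP 9.2.1.2 is weaker than the duration that Appendix D requires. Read literally, it can admit improvement that was lost in between or seen in different lineages. The effect on the HI rate and the CBR can only be upward, and it carries into the choice of subjects and the start date in the DOR analysis that includes HI.

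The size cannot be taken from the documents. With an assumed entry probability of 0.10 it is about 2 to 13 points under persistence. It is larger if entry is more frequent (about 4 to 32 points at 0.20) or if visits are independent, which is close to the worst case. If responses are stable, the effect is small. A reader might quote the independent-visit figures as an expected false-response rate; they rest on an assumed probability and on no carry-over between visits, and the documents support neither.

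For CR, PR and marrow CR the wording has the same gap, partly inherited from Protocol 9.3.1, but it is unlikely to change the count of CR and PR. HI and CBR are secondary and descriptive, and the Stage 1b decision rests on discontinuation and ORR, so this point does not touch it. The rule should be corrected, but it does not threaten the trial's main result.

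**What to change.** Amend SAP 9.2.1.2, and 9.2.1 in parallel:

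- Count a response as confirmed only if no evaluable assessment between the first and the confirming one shows loss of response, relapse or progression. The span is at least 8 weeks in the same lineage for HI, and at least 28 days for CR, PR and marrow CR.
- State what loss of HI means: either no longer meeting the lineage's HI criterion, or meeting the separate Appendix D criteria for relapse after HI. The first is closer to a response that must last.
- Apply the Appendix D exceptions: transient cytopenias during repeated chemotherapy courses and, for HI, also acute infection, gastrointestinal bleeding, hemolysis and similar explanations. Record the reason for each exception applied.
- State that a missed visit does not by itself void a response.
- Keep the any-two rule as a sensitivity table, so that readers can see how much it matters.

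In the same edit, reconcile the SAP's 28 days with the CBC that Protocol 5.2.4 requires at 8 weeks to confirm CR or PR.

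The cost is SAP wording and a little programming. No new data are needed. The reported HI rate and CBR may be somewhat lower.
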